Appendix 5: Experience sampling questions

June 6th 2016

Screening Questions

To ensure that the user research group is comprised of individuals who fit the target audience definition for the app, it could be valuable to consider using screening questions like the following examples to deselect candidates who may not provide value to the research goals:

- Do you own or regularly use a smartphone or tablet?
- Have you used an app within the last six months?

Demographic Questions

How old are you?

What gender are you?

- Male
- Female

How active are you at work?

- Very active
- Somewhat active
- Somewhat inactive
- Very inactive

How much time do you spend seated during your work day?

- 0-2 hours
- 2-4 hours
- 4-6 hours
- 6-8 hours
- 8+ hours

How concerned are you about your sedentary behaviour at work?

- Not concerned
- Somewhat concerned
 - please specify
- Very concerned
 - please specify

Experience Sampling Questions

What apps, websites or personal habits/routines do you currently use to keep you active?

What do you find the most difficult in dealing with your daily activity level?

Can you think of a time/moment when an activity reminder app would have been useful to you?

Does your workplace encourage physical activity?

User Experience & Design Questions

What was main thing that you remember or liked most about the app?

What did you like least about the app?

Was there anything that confused you at first?

Was there anything important to you that was missing?

Do you feel the characters would appeal to you and other people your age?

- Very much agree
- Agree
- Not sure
- Disagree
- Very much disagree

Do you feel the colours and style of the app would appeal to you and other people your age?

- Very much agree
- Agree
- Not sure
- Disagree
- Very much disagree

Do you feel that the available exercises are challenging enough?

- Very much agree
- Agree
- Not sure
- Disagree
- Very much disagree

Do you feel that the available exercises provide enough variety?

- Very much agree
- Agree
- Not sure
- Disagree
- Very much disagree

Did you like the ability to earn “streak points” for completing activities in the app?

- Yes
- No
- Didn't care either way

How likely would you be to consider sharing your progress to friends and family via social media?

- Very likely
- Likely
- Not sure
- Not likely
- Wouldn't at all

How likely would you be to use the app to help support a friend or family member that wanted to be more active during the work day?

- Very likely
- Likely
- Not sure
- Not likely
- Wouldn't at all

Do you feel at least one exercise per hour is achievable?

- Very much agree
- Agree
- Not sure
- Disagree
- Very much disagree

How helpful was it to be reminded via notifications to complete your activity?

- Very helpful
- Helpful
- Not sure
- Not helpful
- Annoying

If you failed to complete an activity, how helpful was it to receive feedback on how to achieve success next time?

- Very helpful
- Helpful
- Not sure
- Not helpful
- Annoying

Did you learn something during the use of this app? If yes, what did you learn?

Appendix 6: Description of experience sampling and Flurry Analytics

Experience sampling:

Experience sampling and marketing validation is a strategic research technique for uncovering user needs and wants. Users are interrupted at defined intervals to note their experience in real-time. The following steps will be taken to gather experience sampling data:

1. Define experience sampling questions based on criteria that focusses on repeated behaviour and avoids yes/no questions, quantity-based answers or opinions.
2. Categorize responses, clean data, adjust categories
3. Generate frequency charts and define themes

Flurry Analytics description

Flurry Analytics is an industry standard that allows researchers and organizations to understand what components of the App the users are most engaged with. It is important to note that individual-level data will not be linked to the user's personal information. Flurry Analytics collects data at the aggregate level. User's IDs are anonymized and are created to pair with the user's device and the server. It is important to note that the user's ID is only known by the server.

Flurry analytics can measure user sessions, frequency of use, session length. Analytics can also determine if the users are progressing through the app as intended, data describing the number of times a specific module of the app was started and how long the user stayed engaged with each module. Flurry is an industry standard analytics tool that measures, tracks and analyzes app performance, user acquisition and activity. Flurry provides a deep understanding of app performance metrics and user behaviour. The following information will be gathered:

- **User sessions**
 - The number of unique users and total number of user sessions - ie 10,000 unique users and 25,000 sessions.
- **Frequency of use**
 - Session frequency distribution for daily, weekly and monthly time periods - ie in a weekly period 2,000 users had 1 session, 4,000 users had 2-3 sessions, 1,500 users had 4-6 sessions
- **Session length**
 - Session length distribution and mean session length - ie median session length is 1.6 minutes, 1,000 users used the app 0-1 min, 2,000 users for 1-3 min, 1,000 users 3-5 min
- **User events**
 - Custom events defined within the app - ie 10,000 users clicked "Save" - or users clicked "Save" and average of 2.6 times per session
- **Technical data and errors**
 - Devices have been used to access the app, number of users who may have experienced a crash (note: false positives for crashes can occur when users close the app and interrupt a process) - ie 5,000 sessions were conducted on Apple iPad Mini WiFi Only
- **Geographic distribution**
 - Reported at a country level

Appendix 7: Poster advertisement

ENCOURAGE Researchers need your help!!!

Sedentary behaviour is becoming increasingly common in the modern working environment. This is concerning, as researchers are beginning to recognize that sitting for extended periods of time increases your risk of diabetes, cardiovascular disease and other adverse health outcomes. Unfortunately, sitting at work is often unavoidable, but we want you to help us change that!

We are seeking volunteers for a research study to test the public release of a mobile app that is designed to decrease sedentary time in the workplace

Are you?

[figure not shown]
- Between the ages of 18 and 70
- An employee of the University of Manitoba or St. Boniface Hospital with a fairly inactive job?
- Consider yourself physically inactive but ready to make a change towards a more active lifestyle?

If you are eligible, seven study visits will be scheduled over 6 months that will include:

- Installing the ENCOURAGE App on your mobile phone (first visit only)
- Wearing a device called an accelerometer to measure your physical activity behavior
- Complete a series of questions regarding your lifestyle behaviors and cardiovascular health risk

You will also be asked to complete weekly questions regarding your experience with the App

If you are interested, please contact us at [contact].

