- 2) The recruitment of a sub-sample of 60 participants who live in Winnipeg, MB which will be drawn from the larger sample of 300 participants and by advertisement. In addition to completing all the components listed above from the recruitment of 300 participants, they will be also asked to wear a physical activity monitor, called an accelerometer.

Inclusion and exclusion criteria

Inclusion criteria:

- Male and female employees 18-70 years old
- Self-identify as being physically inactive in the last 3 months (less than 150 minutes of moderate-vigorous physical activity per week)
- Ready to adopt a more physically active lifestyle based on the Transtheoretical Model¹⁰
- Specific to the sub-sample of 60 participants: Live in Winnipeg, MB

Exclusion criteria:

- Individuals who do not have a personal mobile phone
- Any physical limitations that would not allow a person to engage in physical activity
- Any cognitive limitations that would not allow a person to consent for the study
- Specific to the sub-sample of 60 participants: Those who live outside of Winnipeg, MB.

To our knowledge, no characteristics of the participants make them especially vulnerable or require extra precautions to administer the user observation study. Participants will be healthy volunteers able to provide informed consent.

Participant recruitment

Recruitment of participants involves two phases (Figure 1):

- 1) Recruitment of 300 individuals who download the ENCOURAGE App the iTunes Store or Google play and choose to enroll in the study. Users will be asked via a textbox to determine if they wish to participate in a research project. A description of the project, as well as an electronic consent form will be provided prior to enrolment through Survey Monkey. In order to track participants in the study, we will be asking for their e-mail addresses, their date of birth, and first and last name initials.

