- 2) Recruitment of 60 individuals who live in Winnipeg, MB to wear an accelerometer. We will employ a convenience sampling approach, where participants who are already using the App and participating in the study (i.e., the 300 participants described above) will be asked to participate if they live in Winnipeg. Additionally, we will employ a convenience sampling approach at the St. Boniface Hospital, University of Manitoba, and Tactica Interactive. Participants will be contacted via e-mail. First, we will use an e-mail approach to contact participants. The e-mail approach will provide contact information for potential participants to reach research staff to facilitate the recruitment and consent of participants at a mutually agreeable location. Secondly, we will use a poster advertisement approach (**Appendix 7**) to facilitate recruitment. Posters will be placed around the St. Boniface Hospital, University of Manitoba, and Tactica Interactive. In total for the sub-study, more than 12,000 staff members at the St. Boniface Hospital, 8,700 faculty/staff, at the University of Manitoba, and Tactica Interactive will be accessible, including:
 - Nurses and Nurse Practitioners;
 - Physicians;
 - Property Management (electrical, carpentry, mechanical);
 - Administrators and clerical support staff; and,
 - Researchers
 - Software developers

Study procedures

Large study procedures:

After participants choose to participate in the study, participants will be asked to complete a series of questionnaires at baseline, one week and every month for a total of six months (i.e., 8 different

occasions). The questionnaires (**Appendix 8**) will take approximately 30-45 minutes to complete and comprise of the following:

- 1) Demographics
- 2) Depressive symptoms with the Patient Health Questionnaire-9
- 3) Physical activity using the Godin Leisure Time Exercise Questionnaire
- 4) Cardiovascular health risk using the Cardiovascular Health in Ambulatory Care Research Team (CANHEART) questionnaire
- 5) Occupational Sitting with the Occupational Sitting and Physical Activity Questionnaire
- 6) Self-efficacy levels for physical activity and reducing sedentary time with the Exercise Self-Efficacy Questionnaires and Self-Regulatory Efficacy to Manage Sedentary Behavior questionnaire
- 7) Confidence levels for reducing sedentary behaviors with the Barrier Self-Efficacy to Reduce Sedentary Behavior and Self-efficacy to Reduce Total Daily Sedentary Time questionnaires.

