- 8) Physical activity levels at the workplace with the Workplace Sitting Breaks Questionnaire

Research participants will be prompted within the App to a hyperlink to complete the research questionnaires on Survey Monkey. In order to track individual research participant responses The links are as follows:

- 1) Description of the study/eligibility form, consent to participate, and baseline questionnaire: <https://www.surveymonkey.com/r/L3KDHRQ>
- 2) 1 week survey: <https://www.surveymonkey.com/r/L39CZB5>
- 3) 1 month survey: <https://www.surveymonkey.com/r/L3J2M67>
- 4) 2 month survey: <https://www.surveymonkey.com/r/L3SKXGH>
- 5) 3 month survey: <https://www.surveymonkey.com/r/L3MDLCF>
- 6) 4 month survey: <https://www.surveymonkey.com/r/L3FLMWG>
- 7) 5 month survey: <https://www.surveymonkey.com/r/L3B28KX>
- 8) 6 month survey: <https://www.surveymonkey.com/r/L3P9FGC>

[figure not shown]
Participants will also be asked on two separate occasions over the 6 month period to document their experiences using an experience sampling approach. A list of questions used are in **Appendix 5**.

Sub-study procedures:

Participants from Winnipeg, MB who choose to enroll in the sub-study will complete the study procedures for the large study and will also be asked to meet with research staff to obtain consent for the smaller study and will be asked to wear an accelerometer for 7-day periods at baseline and every month for 6 months (i.e., 7 different occasions). The research appointments will last approximately 30 minutes each.

See below for a figure overviewing the flow of the study.

Figure 1. Study flow chart

Assessment of Safety

Since this is not a drug study, rescue medication is not warranted. Should any participant experience adverse effects as a consequence of participation in the study, they will be excluded from the study and receive routine clinical care. All serious adverse events as well as death due to any cause or cardiovascular death will be reviewed by the medical monitor within 24 hrs of becoming aware of events. Any Serious Adverse Events will be reported to the University of Manitoba Health Ethics Boards and St. Boniface Hospital.

Statistics

Sample Size

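### For new recruits to the accelerometer sub-study, the stated schedule has no wear week before the App is on the phone, so the pre value may already include App exposure

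*Protocol*

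**What the plan says.** **Visits and installation.** The poster (Protocol, Appendix 7) says "seven study visits will be scheduled over 6 months that will include" three things: "Installing the ENCOURAGE App on your mobile phone (first visit only", wearing the accelerometer, and answering questionnaires.

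**Wear periods.** Under Sub-study procedures, participants "wear an accelerometer for 7-day periods at baseline and every month for 6 months (i.e., 7 different occasions". The same paragraph says they "will also be asked to meet with research staff to obtain consent for the smaller study". It does not say when the App goes on the phone.

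**Questionnaires.** Under Study procedures, "Research participants will be prompted within the App to a hyperlink to complete the research questionnaires on Survey Monkey". The link list there includes one for eligibility, consent and the baseline questionnaire.

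**Who the 60 are.** Trial design says the sub-sample will be "drawn from the larger sample of 300 participants and by advertisement". Participant recruitment asks Winnipeg residents who already use the App, and adds convenience sampling at three named sites: "First, we will use an e-mail approach to contact participants", then posters.

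**Outcomes.** The protocol (Sample Size) makes change in moderate-vigorous activity in these 60 the primary outcome. It is sized on a rise from 72 to 92 min/week. The SAP names a different primary outcome, breaks in sedentary time from baseline to one month, and gives no instrument for it.

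**The concern.** The design has no control group, so the baseline week is the only comparator. The App prompts activity at intervals that the user sets (Trial design), so it could act from its first day. If the baseline monitor is worn with the App already running, any early response becomes part of the pre value. The pre/post change then understates the difference between using the App and not using it.

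New recruits matter most here. Sub-study members drawn from the 300 are App users before their accelerometer baseline, so only new recruits could supply an App-free week. Neither the protocol's Statistics section nor the SAP can recover such a week by analysis if it was never recorded.

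**Working it through.** **1. Schedule**

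| Source | Count | Content |
|---|---|---|
| Appendix 7 | 7 visits over 6 months | App installed at visit 1 only |
| Sub-study procedures | 1 baseline + 6 monthly = 7 wear periods | 7 days each |

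Seven visits for seven wear periods makes visit 1 the baseline occasion. A monitor records forward from the day it is issued. Neither document describes an earlier visit, a mailed monitor, a run-in week or delayed activation. In-App prompting to the questionnaires fits with the App being on the phone at baseline. No single sentence states the order; it comes from reading the two places together.

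**2. The plan's own sample size**

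Inputs (Protocol, Sample Size): SDs 64 and 86 min/week, correlation 0.8, difference 20 min/week, two-tailed α 0.05, power 80%, stated n = 44.

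- SD of change = √(64² + 86² − 2 × 0.8 × 64 × 86) = √(4096 + 7396 − 8806.4) = √2685.6 = 51.8
- Normal approximation: n = (51.8 × (1.960 + 0.842) / 20)² = 52.7, so 53. The paired t-test gives 55.

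The stated 44 is not reproduced. A one-sided test comes close (42 normal, 43 t), as does a common SD of about 75 (44.2 before rounding up). That mismatch is a separate matter. With the stated inputs, two-sided paired-t power is 71% at n = 44 and 84% at n = 60.

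**3. Illustration of dilution**

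Let f be the fraction of the 20 min/week already present in the baseline week, and q the share of the 60 affected. Neither is in the documents. The mean measurable change is 20 × (1 − q × f). The SD of change is held at 51.8.

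| q | f | Change (min/week) | Power, n = 60 | Power, n = 44 |
|---|---|---|---|---|
| any | 0 | 20 | 84% | 71% |
| 1 | 0.25 | 15 | 60% | 47% |
| 1 | 0.5 | 10 | 31% | 24% |
| 0.5 | 0.25 | 17.5 | 73% | 59% |
| 0.5 | 0.5 | 15 | 60% | 47% |

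The n = 60 column assumes no dropout, although the protocol sets 60 to allow for it. The n = 44 column is what remains if 16 drop out. The q = 0.5 rows give the other half the full 20 min/week. That is generous if those people were already using the App.

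**The case against.** The strongest reply is that this is an inference from a recruitment poster. The poster lists what the visits contain. It does not order installation against wear, and it gives no hand-out date. Sub-study procedures is the operative text and is silent on installation. It refers to a flow chart (Figure 1) that could not be read here and might show the order. This stands as a limit on confidence.

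Other limits also stand:

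- **Installed is not the same as exposed.** Users set their own prompts, and nothing says that prompts run in the first wear week. A reader might infer that the pre value simply is the first week of prompting. The documents do not go that far.
- **Size of f.** The example activities include a neck stretch and standing to read, so a small first-week effect on moderate-vigorous activity fits the text as well as a large one. A reader might also infer that novelty could reverse the sign of the change. Nothing in the documents supports that.
- **E-mail recruits.** The installation wording is in the poster only. Extending it to new e-mail recruits rests on their entering the same seven-occasion schedule.
- **Share affected.** The split of the 60 by route is not stated, so the rows with all 60 affected are an extreme case.
- **SAP outcome.** If breaks in sedentary time come from the Workplace Sitting Breaks Questionnaire, which asks about a typical work day, the accelerometer timing does not touch the SAP's primary outcome.

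None of these supplies an App-free wear week. They bear on how large the problem is and how certain, but the stated schedule still contains no such week.

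**Conclusion.** The concern holds in a limited form. Followed as written, the schedule for poster recruits, and by inference for new e-mail recruits, puts the App on the phone no later than the visit that starts the baseline wear. The protocol's primary pre/post change may therefore be diluted, by an amount the documents cannot give. The power figures are illustrations that depend on assumed f and q; they are not estimates of the loss. If f is zero there is no loss, but the plan does nothing to ensure that.

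Confidence is medium, because the order comes from joining two sections and Figure 1 could not be read. The point reaches the SAP's primary outcome only if that outcome is measured by accelerometer. It should be settled before the first sub-study visit, because a missed App-free week cannot be collected later.

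**What to change.** In Sub-study procedures and Appendix 7, for newly recruited sub-study participants:

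1. At visit 1, take consent and issue the monitor. Install or activate the App only after the 7-day baseline wear ends.
2. Record that date as time zero for the 1-week survey and for months 1 to 6.
3. Give the screening form and baseline questionnaire by the existing web link, because they are otherwise reached through the App.

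For all 60, record the recruitment route and App start date. Report the pre/post change in participants with an App-free baseline separately from those without one. Changing the order for new recruits does not alter the baselines of members already using the App, and pooling would mix two kinds of pre value.

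**Cost.** App start is delayed by about one week, and the install date must be confirmed person by person, since the App analytics are aggregate only. Separate reporting also makes each group smaller. On the plan's own inputs, a group of fewer than 55 completers has less than 80% power for 20 min/week. The sponsor should therefore consider how many of the 60 will come from new recruitment.

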Appendix 8: Study questionnaire package

Appendix List of questionnaires

1. Demographics Questionnaire
2. Patient Health Questionnaire-9
3. Occupational Sitting and Physical Activity Questionnaire
4. Godin leisure time exercise questionnaire
5. The Cardiovascular Health in Ambulatory Care Research Team (CANHEART) health questionnaires
 - CANHEART Questionnaire – Tobacco use
 - CANHEART Questionnaire – Fruit and vegetable consumption
 - CANHEART Questionnaire – High blood pressure
 - CANHEART Questionnaire – Diabetes
6. Exercise Self-Efficacy Questionnaires:
 - Physical Activity Task Self-Efficacy Questionnaire
 - Physical Activity Self-Regulatory Efficacy Questionnaire
7. Self-Regulatory Efficacy to Manage Sedentary Behavior
8. Barrier Self-Efficacy to Reduce Sedentary Behavior
9. Self-efficacy to Reduce Total Daily Sedentary Time
10. Workplace Sitting Breaks Questionnaire

PHQ-9 QUESTIONNAIRE

Over the past 2 weeks, how often have you been bothered by any of the following problems? Please circle the best response, according to the following scale:

	0	1	2	3
	Not at all	Several days	More than half the days	Nearly every day
	Not at all	Several days	More than half the days	Nearly every day
1. Little interest or pleasure in doing things	0	1	2	3
2. Feeling down, depressed or hopeless	0	1	2	3
3. Trouble falling or staying asleep, or sleeping too much	0	1	2	3
4. Feeling tired or having little energy	0	1	2	3
5. Poor appetite or overeating	0	1	2	3
6. Feeling bad about yourself – or that you are a failure or have let yourself or your family down	0	1	2	3
7. Trouble concentrating on things, such as reading the newspaper or watching television	0	1	2	3
8. Moving or speaking so slowly that other people could have noticed. Or the opposite – being so fidgety or restless that you have been moving around a lot more than usual	0	1	2	3
9. thoughts that you would be better off dead, or of hurting yourself in some way	0	1	2	3
10. If you checked off any problems, how difficult _____ have these problems made it for your to do your _____ work, take care of things at home, or get along _____	Not difficult at all Somewhat difficult Very difficult			

with other people?

Extremely difficult

please check (✓) your response

OCCUPATIONAL SITTING AND PHYSICAL ACTIVITY QUESTIONNAIRE (OSPAQ)

1. How many hours did you work in the last 7 days? _____ hours
2. During the last 7 days, how many days were you at work? _____ days
3. How would you describe your typical work day in the last 7 days? (This involves only your work day, and does not include travel to and from work, or what you did in your leisure time)

a. Sitting (including driving)	_____ %
b. Standing	_____ %
c. Walking	_____ %
d. Heavy labour or physically demanding tasks	_____ %
Total	_____ %

Example:

Jane is an administrative officer. Her work day involves working on the computer at her desk, answering the phone, filing documents, photocopying, and some walking around the office.

Jane would describe a typical work day in the last 7 days like this:

Sitting (including driving)	90 %
Standing	5 %
Walking	5 %
Heavy labour or physically demanding tasks	0 %
Total	100 %

GODIN LEISURE TIME EXERCISE QUESTIONNAIRE

INSTRUCTIONS

In this excerpt from the Godin Leisure-Time Exercise Questionnaire, the individual is asked to complete a self-explanatory, brief four-item query of usual leisure-time exercise habits.

CALCULATIONS

For the first question, weekly frequencies of strenuous, moderate, and light activities are multiplied by nine, five, and three, respectively. Total weekly leisure activity is calculated in arbitrary units by summing the products of the separate components, as shown in the following formula:

$$\text{Weekly leisure activity score} = (9 \times \text{Strenuous}) + (5 \times \text{Moderate}) + (3 \times \text{Light})$$

The second question is used to calculate the frequency of weekly leisure-time activities pursued “long enough to work up a sweat” (see questionnaire).

EXAMPLE

Strenuous = 3 times/wk

Moderate = 6 times/wk

Light = 14 times/wk

$$\text{Total leisure activity score} = (9 \times 3) + (5 \times 6) + (3 \times 14) = 27 + 30 + 42 = 99$$

1. During a typical 7-Day period (a week), how many times on the average do you do the following kinds of exercise for more than 15 minutes during your free time (write on each line the appropriate number).

a) STRENUOUS EXERCISE (HEART BEATS RAPIDLY)

(e.g., running, **jogging**, hockey, football, soccer, squash, basketball, cross country skiing, judo, roller skating, vigorous swimming, vigorous long distance bicycling)

TIMES PER WEEK _____

b) MODERATE EXERCISE (NOT EXHAUSTING)

(e.g., fast walking, baseball, tennis, easy bicycling, volleyball, badminton, easy swimming, alpine skiing, popular and folk dancing)

TIMES PER WEEK _____

c) MILD EXERCISE (MINIMAL EFFORT) (e.g., yoga, archery, fishing from river bank, bowling, horshoes, golf, snow-mobiling, easy walking)

TIMES PER WEEK _____

2. During a typical 7-Day period (a week), in your leisure time, how often do you engage in any regular activity long enough to work up a sweat (heart beats rapidly)?

OFTEN

SOMETIMES

NEVER/RARE

1.

2.

3.

CANHEART QUESTIONNAIRE – TOBACCO USE

1. Never used tobacco: 2. Ex-tobacco user: Quit date _____ 3.

Currently use:

If tobacco user, average number per day _____ and number of years _____

CANHEART QUESTIONNAIRE – FRUIT AND VEGETABLE CONSUMPTION

The next questions are about the foods you usually eat or drink. Think about all the foods you eat, both meals and snacks, at home and away from home.

1. How often do you usually drink fruit juices such as orange, grapefruit or tomato? (for example, once a day, three times a week, twice a month)

Times/day _____ OR Times/week _____

2. Not counting juice, how often do you usually eat fruit?

Times/day _____ OR Times/week _____

3. How often do you (usually) eat green salad?

Times/day _____ OR Times/week _____

4. How often do you usually eat potatoes, not including French fries, fried potatoes, or potato chips?

Times/day _____ OR Times/week _____

5. How often do you (usually) eat carrots?

Times/day _____ OR Times/week _____

6. Not counting carrots, potatoes, or salad, how many servings of other vegetables do you usually eat?

Times/day _____ OR Times/week _____

CANHEART QUESTIONNAIRE – HIGH BLOOD PRESSURE

1. We're interested in conditions diagnosed by a healthcare professional. Do you have high blood pressure? (please circle one)

Yes No

2. If yes, how old were you when you were first diagnosed?

Age in years _____

CANHEART QUESTIONNAIRE - DIABETES

1. We're interested in conditions diagnosed by a healthcare professional. Do you have diabetes? (please circle one)

Yes No

2. If yes, how old were you when you were first diagnosed?

Age in years _____

EXERCISE SELF-EFFICACY QUESTIONNAIRES**PHYSICAL ACTIVITY TASK SELF-EFFICACY QUESTIONNAIRE**

How certain are you that you can engage in moderate- to strenuous-intensity physical activity for the following durations? Please rate your degree of confidence for each duration using the scales.

10 minutes

0	1	2	3	4	5	6	7	8	9	10
Cannot at all certain				Moderately						Highly
				can do						can do

20 minutes

0	1	2	3	4	5	6	7	8	9	10
Cannot at all certain				Moderately						Highly
				can do						can do

30 minutes

0	1	2	3	4	5	6	7	8	9	10
Cannot at all certain				Moderately						Highly
				can do						can do

40 minutes

0	1	2	3	4	5	6	7	8	9	10
Cannot at all certain				Moderately						Highly
				can do						can do

50 minutes

0	1	2	3	4	5	6	7	8	9	10
Cannot at all certain				Moderately						Highly
				can do						can do

60 minutes

0	1	2	3	4	5	6	7	8	9	10
Cannot at all certain				Moderately						Highly
				can do						can do

PHYSICAL ACTIVITY SELF-REGULATORY EFFICACY QUESTIONNAIRE

Please rate your confidence in your ability to engage in the following behaviours over the next 8 weeks.

1. Over the next 8 weeks, how confident are you that you can identify key factors that trigger lapses in your physical activity?

0	1	2	3	4	5	6	7	8	9	10
Not at all				Moderately						
Completely				confident						
confident				confident						

2. Over the next 8 weeks, how confident are you that you can arrange your schedule in order to do your physical activity no matter what?

0	1	2	3	4	5	6	7	8	9	10
Not at all				Moderately						
Completely				confident						
confident				confident						

3. Over the next 8 weeks, how confident are you that you will set realistic physical activity goals?

0	1	2	3	4	5	6	7	8	9	10
Not at all				Moderately						
Completely				confident						
confident				confident						

4. Over the next 8 weeks, how confident are you that you will develop solutions to cope with potential barriers that can interfere with your physical activity?

0	1	2	3	4	5	6	7	8	9	10
Not at all				Moderately						
Completely				confident						
confident				confident						

5. Over the next 8 weeks, how confident are you that you can make up times when you miss your physical activity sessions?

0 1 2 3 4 5 6 7 8 9 10

Not at all Moderately
Completely confident confident confident

6. Over the next 8 weeks, how confident are you that you will follow through with your physical activity for the week, even though it may be difficult at times?

0 1 2 3 4 5 6 7 8 9 10

Not at all Moderately
Completely confident confident confident

7. Over the 8 weeks, how confident are you that you will organize your time and responsibilities around each physical activity session no matter what?

0 1 2 3 4 5 6 7 8 9 10

Not at all Moderately
Completely confident confident confident

8. Over the next 8 weeks, how confident are you that you will resume your physical activity when it is interrupted and you miss physical activity for a few days or weeks?

0 1 2 3 4 5 6 7 8 9 10

Not at all Moderately
Completely confident confident confident

9. Over the 8 weeks, how confident are you that you can schedule your physical activity around your daily activities?

0 1 2 3 4 5 6 7 8 9 10

Not at all Moderately
Completely confident confident confident

10. Over the next 8 weeks, how confident are you that you will develop plans to reach your level of physical activity?

0	1	2	3	4	5	6	7	8	9	10
Not at all				Moderately						
Completely				confident						
confident				confident						

11. Over the next 8 weeks, how confident are you that you will view any missed physical activity as challenges to overcome rather than failures?

0	1	2	3	4	5	6	7	8	9	10
Not at all				Moderately						
Completely				confident						
confident				confident						

12. Over the next 8 weeks, how confident are you that you can set realistic goals for maintaining your level of physical activity?

0	1	2	3	4	5	6	7	8	9	10
Not at all				Moderately						
Completely				confident						
confident				confident						

13. Over the next 8 weeks, how confident are you that if you do not do your exercise for a few days, you can readjust your goals to resume physical activity?

0	1	2	3	4	5	6	7	8	9	10
Not at all				Moderately						
Completely				confident						
confident				confident						

Self-Regulatory Efficacy to Manage Sedentary Behaviour

You may have heard that being sedentary, or sitting too much is bad for our health. We would like to know about your confidence to be able to do certain things that would promote reductions in sedentary behaviour (sitting time) at work.

Using the scale below, choose a number that best represents how **confident** you are that you could do the things listed in the table below during your work day.

0	10	20	30	40	50	60	70	80	90	100
Not at all confident			Moderately confident				Completely confident			

How confident are you that you can...

Make sitting less a priority?	
Schedule in regular standing/movement breaks, especially during long bouts of sitting (i.e., sitting bouts that last for more than one hour)?	
Stick to a schedule that has been designed to help you spend less time sitting?	
Keep track of the time you spend sitting every day?	
Identify factors (people, places, things) that influence the amount of time you spend sitting on a daily basis?	
Identify situations and settings in which you could stand up or move instead of sitting still?	
Set realistic goals for sitting less (e.g., sit less by 30 minutes a day)?	
Identify barriers and challenges that might prevent you from being able to spend less time sitting?	
Develop strategies and solutions to overcome barriers and challenges that prevent you from sitting less?	
Restart your efforts to sit less even if you fail to meet your goals for sitting less for a few days?	

Barrier Self-Efficacy to Reduce Sedentary Behaviour

We are interested in your confidence to reduce your sedentary behaviour (sitting time) when facing certain barriers and challenges that might interfere with your ability to sit less at work.

Using the scale below, choose a number that best represents how confident you are that you could reduce your sitting time at work when faced with each of the barriers listed in the table below.

0	10	20	30	40	50	60	70	80	90	100
Not at all confident			Moderately confident				Completely confident			

How confident are you that you can reduce the amount of time you spend sitting (i.e., by taking regular standing/movement breaks), even if you...

Are feeling tired (physically and/or mentally)	
Are feeling comfortable and relaxed in your seated position	
Have important tasks to do that require you to be seated (e.g., study, using a computer)	
Feel like you deserve to sit down	
Feel stressed out	
Feel down or depressed	

Self-Efficacy to Reduce Total Daily Sedentary Time

We are interested to know how confident you are to reduce your total daily sitting time.

Using the scale provided, choose the number that best represents how confident you are to reduce your total daily sitting time by the time durations listed in the table below. Remember to consider all of time you spend sitting on a typical day (e.g., at home, school, work, and in transportation).

0	10	20	30	40	50	60	70	80	90	100
Not at all confident			Moderately confident				Completely confident			

Over the next 7 days, how confident are you that you can reduce the total time you spend sitting per day by the following durations...

10 minutes	
30 minutes	
1 hour	
1.5 hours	
2 hours	
More than 2 hours	

WORKPLACE SITTING BREAKS QUESTIONNAIRE (SITBRQ)**Short Physical Activity Breaks = any interruption to sitting time at work**

One area we wish to explore is whether you take breaks from your working tasks during work hours. During a typical working day there may be opportunities to take short physical activity breaks from your working tasks. This is any interruption to your sitting time at work. For example, taking time away from your desk/workstation to move around perhaps to get a drink, have a bathroom break or even continuing a work task while standing.

How many breaks from sitting (such as standing up, or stretching or taking a short walk) during one hour of sitting would you typically take at work?
(please circle the correct answer to the following questions)

a. During a typical work day how many breaks from sitting (such as standing up, or stretching or taking a short walk) during one hour of sitting would you take at work ?	6 or more	5	4	3	2	1	0
b. What is the total time you spend in short physical activity breaks during a typical day at work?	60 minutes or more	30- 59 min	20- 29 min	10- 19 min	5-9 min	Less than 5 min	N/A
